6.11 Supportive Therapy

6.11.1 All patients will be adequately hydrated and receive appropriate anti-emetics based upon institutional guidelines.

6.11.2 Additional growth factors may be used according to institutional practice guidelines or the preference of the attending physician.

6.11.3 Antimicrobial prophylaxis should be used according to institutional practice guidelines. In case of neutropenic fever, standard diagnostic testing will be performed, and empiric antibiotic coverage will be utilized as per usual care and standard institutional practices.

6.11.4 Transfusional support should be carried out according to institutional practice guidelines.

6.12 Treatment of CNS Disease

Treatment of CNS disease is done according to institutional practice guidelines or the preference of the attending physician.

6.13 Recommended Follow-up Care

6.13.1 For patients who continue to receive sorafenib for up to 12 months after the completion of G-CLA+sorafenib, they should have complete blood counts and a metabolic panel (to include kidney and liver function) done at least monthly and a bone marrow exam every 3 months, including after the completion of sorafenib.

6.13.2 While still on sorafenib, blood pressure should be monitored at least monthly.

6.13.3 After completion of protocol treatment, patients should be evaluated by treating physicians according to institutional and/or national guidelines or the discretion of the attending physician. These evaluations may include peripheral blood studies and/or bone marrow examinations, as clinically indicated.

6.14 Criteria for Removal from Treatment

All reasons for discontinuation of treatment must be documented:

6.14.1 Completion of protocol treatment.

6.14.2 HCT after achievement of CR.

6.14.3 Initiation of any other leukemia-directed therapy other than protocol therapy

6.14.4 Failure to achieve MRDneg CR after 3 courses of therapy.

6.14.5 Persistent aplasia (ANC <500/ μ L or platelets <50,000/ μ L) without evidence of leukemia after Day +49.

6.14.6 Relapse (including recurrence of MRD) after achievement of CR during treatment.

6.14.7 Adverse toxicities that prevent continuation with study treatment.

6.14.8 Withdrawal of consent; the patient may withdraw from the study at any time for any reason.

7.0 INFORMATION ON STUDY DRUGS

G-CSF, cladribine, cytarabine and mitoxantrone will be obtained commercially.

Sorafenib will be provided free of charge by Bayer HealthCare Pharmaceuticals.

7.1 Drug Information on G-CSF (Granulocyte colony-stimulating factor)

7.1.1 Mechanism of Action: G-CSF is a growth factor that stimulates the production, maturation, and activation of neutrophils. Further, it promotes premature release of neutrophils from the bone marrow and enhances their phagocytic capacity.

7.1.2 Pharmacokinetics: Peak G-CSF concentrations after sub-cutaneous dosing occur in 2 to 8 hours, though the onset of action is approximately 24 hours, with plateau concentrations in 3-5 days, and elimination over an 11-20 day period. G-CSF is cleared by systemic degradation. Notably, as G-CSF binds neutrophils, plasma levels are controlled in large part by the absolute neutrophil count.[31]

7.1.3 Adverse Effects (AEs): *Common drug-related AEs (occurring in >10% of patients)* include fever, petechiae, elevated uric acid, splenomegaly, bone pain, and epistaxis. *Less common drug-related AEs (occurring in 1% -10% of patients)* include hyper- or hypotension, arrhythmias, headache, nausea, vomiting, leukocytosis, and transfusion reaction. *Infrequent drug-related AEs (occurring in <1% of patients)* include acute respiratory distress syndrome, allergic reactions, alopecia, alveolar hemorrhage, arthralgia, bone density decrease, capillary leak syndrome, cerebral hemorrhage, vasculitis, dyspnea, edema, erythema nodosum, hematuria, hemoptysis, hepatomegaly, hypersensitivity, injection site reaction, pericarditis, proteinuria, psoriasis exacerbation, pulmonary infiltrates, renal insufficiency, sickle cell crisis, splenic rupture, Sweet's syndrome, tachycardia, and thrombophlebitis.

7.1.4 Recommended dose adjustments for organ dysfunction: There is limited or no data examining the toxicity of G-CSF in patients with renal or liver dysfunction. Therefore, administration of G-CSF to patients with liver or kidney disease must be done with caution.

7.2 **Drug Information on Cladribine (2-chloro-2'-deoxyadenosine, 2-CdA)**

7.2.1 Mechanism of Action: Cladribine is a prodrug that is converted to an adenosine deaminase-resistant triphosphate derivative (2-CdATP). This molecule is then activated by deoxycytidine kinase to a 5'-triphosphate derivative (2-CdAMP), which is incorporated into DNA where it acts as a transcription regulator. In addition to its cytotoxic properties in dividing cells, cladribine induces death in quiescent cells of lymphoid origin through an unknown mechanism.[32]

7.2.2 Pharmacokinetics: Cladribine is renally excreted, with 18-35% as unchanged drug. It is able to penetrate the CSF, where it achieves 25% of plasma concentrations. It is 20% protein-bound. The half-life for elimination after a 2-hour infusion is 6.7 ± 2.5 hours in patients with normal renal function.

7.2.3 Adverse Effects: *Common adverse effects (occurring in >10% of patients)* include fever, fatigue, headache, rash, nausea, anorexia, vomiting, myelosuppression (including grade 3/4 neutropenia/thrombocytopenia), injection site reaction, and infection. *Less common adverse effects (occurring in 1 to 10% of patients)* include edema, tachycardia, thrombosis, chills, dizziness, insomnia, malaise, diarrhea or constipation, weakness, myalgias and arthralgias, cough, dyspnea, epistaxis, and diaphoresis. *Rare adverse effects (occurring in <1% of patients)* include aplastic anemia, bacteremia, opportunistic infections, lymphocytopenia, altered mental status, hemolytic anemia, hypersensitivity, myelodysplastic syndrome, quadriplegia, and renal dysfunction/failure.

7.2.4 Reconstitution: Cladribine is supplied as a sterile, preservative-free, isotonic solution containing 10 mg of cladribine (1 mg/mL) in 10 mL single-use vials.

Cladribine should be passed through a sterile 0.22 μ m filter prior to introduction into the infusion bag containing 0.9% Sodium Chloride Injection, USP.

7.2.5 Administration and Compatibility: The use of 5% dextrose is not recommended as a diluent because of increased degradation of cladribine. The infusion solution is stable for 24 hours at room temperature.

7.2.6 Storage and Stability: Store refrigerated 2° to 8°C (36° to 46°F). Protect from light during storage.

7.2.7 Recommended Dose Adjustments for Organ Dysfunction: Specific guidelines for cladribine dosing in patients with hepatic/renal dysfunction or hypoalbuminemia are not clearly defined. Because of the potential for compensatory elimination of cladribine in patients with hepatic and/or renal dysfunction, specific guidelines for dosing are difficult to define. Thus, when deciding whether to adjust cladribine doses for renal dysfunction, the risks for potential toxicities (e.g., myelosuppression, neurotoxicity) against the benefits and goals of treatment must be considered.

7.3 Drug Information on Cytarabine (Cytosine arabinoside)

7.3.1 Mechanism of Action: Cytarabine is a synthetic pyrimidine analog, in which the sugar moiety (normally a ribose or deoxyribose) has been replaced with arabinose. Although its mechanism of action is not completely understood, the active form of cytarabine is probably incorporated into the DNA and interferes with DNA synthesis. As such, cytarabine has been found to primarily effect dividing cells, blocking their progression from G₁ to S phase.

7.3.2 Pharmacokinetics: Cytarabine is metabolized by deoxycytidine kinase and other kinases into its most active form (aracytidine triphosphate). Aracytidine triphosphate is converted to nontoxic uracil derivatives by pyrimidine nucleoside deaminases. This balance between the levels of kinases and deaminases is critical for regulating the sensitivity/resistance of cells to the drug. The plasma clearance of cytarabine is biphasic, with an initial rapid phase and more prolonged second clearance phase. The rapid clearance phase has a relatively short half-life ($t_{1/2\alpha} = 10$ minutes), while the half-life of the second clearance phase is slightly longer ($t_{1/2\beta} = 1 - 3$ hours). The nontoxic metabolites from the drug are excreted in the urine, and within 24 hours after the infusion, approximately 80% of these nontoxic metabolites can be recovered from the urine.

7.3.3 Adverse Effects: The dose-limiting toxicity for cytarabine is myelosuppression. *Adverse Events Associated with Standard Dose Cytarabine: Frequent AEs (not definitely quantified)* include the following: myelosuppression (leucopenia, anemia, neutropenia, thrombocytopenia), pyrexia, rash, anorexia, diarrhea, nausea, vomiting, mucositis, anal inflammation or ulceration, hepatic dysfunction or increased liver enzymes, and local thrombophlebitis. *Less frequent AEs (not definitely quantified)* include chest pain, pericarditis, dyspnea, dizziness, headache, neural toxicity, neuritis, alopecia, pruritis, skin freckling, skin ulceration, urticaria, abdominal pain, bowel necrosis, esophageal ulceration, esophagitis, pancreatitis, sore throat, urinary retention, jaundice/hyperbilirubinemia, local site cellulites, renal dysfunction, allergic edema or anaphylaxis, sepsis, and sudden

respiratory distress syndrome. *Infrequent AEs (not definitely quantified)* include aseptic meningitis, cardiopulmonary arrest, cerebral dysfunction, cytarabine syndrome (bone pain, chest pain, conjunctivitis, fever, maculopapular rash, malaise, myalgia), exanthematous pustulosis, hyperuricemia, intestinal pneumonitis, increased lipase, paralysis with intrathecal and IV combination therapy, rhabdomyolysis, veno-occlusive disorder, and death. *Adverse Events Associated with High Dose Cytarabine* include cardiomegaly and cardiomyopathy, coma, severe neurotoxicity, personality change, somnolence, total body alopecia, severe rash or skin desquamation, gastrointestinal ulceration, peritonitis, intestinal pneumatosis, necrotizing colitis, liver abscess or damage, peripheral neuropathy, corneal toxicity, hemorrhagic conjunctivitis, pulmonary edema, sudden respiratory distress syndrome, and sepsis.

- 7.3.4 **Reconstitution:** Cytarabine should be reconstituted in sterile water and can be further diluted using either 5% dextrose or sodium chloride solutions into appropriate concentrations for infusion.
- 7.3.5 **Administration and Compatibility:** The diluted cytarabine solution should be inspected for particulate matter, discoloration, and haze prior to infusion. If there is evidence of particulate matter, discoloration, or haze the solution should not be infused. Patients should be medicated with standard anti-emetic therapy. Cytarabine is not compatible (1) during Y-site administration with allopurinol, amphotericin B, ganciclovir; (2) in syringe with metoclopropamide; or (3) admixed with fluorouracil, heparin, insulin (regular), nafcillin, oxacillin, penicillin G. Cytarabine may have variable compatibility when admixed with gentamycin, hydrocortisone, and methylprednisolone.
- 7.3.6 **Storage and Stability:** Vials of non-reconstituted cytarabine should be stored at room temperature 15°C - 30°C (59°F - 86°F). The diluted cytarabine solution may be stable for up to 48 hours if stored at room temperature.
- 7.3.7 **Drug-Drug Interaction:** Reversible decreases in the plasma steady-state concentration for digoxin and cardiac glycosides may occur. Cytarabine may diminish the therapeutic effect of flucytosine. There is *ex vivo* data suggesting that cytarabine may reduce the effectiveness gentamycin for killing *K. pneumoniae*.
- 7.3.8 **Warnings and Precautions:** *Ex vivo* and *in vivo* studies have found that cytarabine causes extensive chromosomal damage and potential malignant transformation. Although there have been some case reports describing cytarabine use in pregnant humans, these cases reports are few. Thus, cytarabine is considered Pregnancy Category D. Women should be advised not to become pregnant while receiving cytarabine, and men should be advised not to father a child while receiving cytarabine and for at least 3 months after completing the therapy. It is not known whether cytarabine or its metabolites are excreted in breast milk; thus, it is not recommended for lactating females who are breast-feeding. As with any highly immunosuppressive medication, cytarabine may diminish the effectiveness of dead and live vaccines and enhance the toxic/adverse effect of live vaccines. One should avoid use of live vaccines while receiving it. A small percentage of patients will have a hypersensitivity reaction to cytarabine, and these individuals should not receive the drug again.

7.3.9 Recommended Dose Adjustments for Organ Dysfunction: Guidelines for adjusting cytarabine dose due to renal or liver dysfunction are not standardized, but many clinicians will adjust the dose based upon the function of these organs.

7.4 Drug Information on Mitoxantrone

7.4.1 Mechanism of Action: Mitoxantrone (dihydroxyanthracenedione) is an anthracenedione derivative that intercalates with DNA, resulting in inhibition of nucleic acid synthesis.

7.4.2 Pharmacokinetics: Mitoxantrone is 78% bound to plasma proteins. A three-compartment model was described after a single intravenous dose of mitoxantrone. The mean alpha half-life is 6 to 12 minutes, the mean beta half-life is 1.1 to 3.1 hours, and the mean terminal (gamma) or elimination half-life is 23 to 215 hours (median 75 hours). Mitoxantrone has extensive distribution into body tissues and is metabolized in the liver to two main inactive metabolites (monocarboxylic acid derivative and dicarboxylic acid derivative). The major route of excretion for mitoxantrone appears to be biliary into the feces; approximately 11% of the dose is recovered in the urine within 5 days of drug administration, with 65% of this being unchanged drug.

7.4.3 Adverse Effects: *Common adverse effects (occurring in >10% of patients)* include edema, fever, fatigue, headache, alopecia, nausea/vomiting, diarrhea, mucositis/stomatitis, myelosuppression, weakness, dyspnea, cough, and infection. *Less common adverse effects (occurring in 1 to 10% of patients)* include congestive heart failure, decreased left ventricular ejection fraction (LVEF), hypertension, chills, anxiety, cutaneous mycosis, hypocalcemia, hypokalemia, hyponatremia, menorrhagia, jaundice, myalgia, arthralgia, renal failure, proteinuria, rhinitis, diaphoresis, and infection.

Mitoxantrone may cause cardiac toxicity with prolonged administration and doses exceeding 80 to 100 mg/m²; Appendix B provides an overview of the cardiotoxicity index of individual anthracyclines as well as mitoxantrone. When used after doxorubicin, cardiotoxicity is more frequent; an analysis by the Southwest Oncology Group revealed a risk of 6% at 134 mg/m² prior doxorubicin and 60 mg/m² mitoxantrone, rising to a 15% risk at 120 mg/m² mitoxantrone. Cardiac events reported included arrhythmias, decreased left ventricular function, chronic heart failure, tachycardia, ECG changes, and, infrequently, myocardial infarction. Bradycardia has been rarely reported. Patients with prior treatment with anthracyclines, prior mediastinal radiotherapy, or with preexisting cardiovascular disease may have more frequent occurrences of cardiac toxicity.

7.4.4 Reconstitution: Mitoxantrone must be diluted prior to use. The dose of mitoxantrone should be to at least 50 mL with either 0.9% Sodium Chloride Injection (USP) or 5% Dextrose Injection (USP). Mitoxantrone may be further diluted into Dextrose 5% in Water, Normal Saline or Dextrose 5% with Normal Saline and used immediately.

7.4.5 Administration and Compatibility: Care in the administration of mitoxantrone will reduce the chance of extravasation. Mitoxantrone should be administered into the tubing of a freely running intravenous infusion of 0.9% Sodium Chloride

Injection, USP or 5% Dextrose Injection, USP. Care should be taken to avoid extravasation at the infusion site and to avoid contact of mitoxantrone with the skin, mucous membranes, or eyes. If any signs or symptoms of extravasation have occurred, including burning, pain, pruritis, erythema, swelling, blue discoloration, or ulceration, the injection or infusion should be immediately terminated and restarted in another vein.

Mitoxantrone should not be mixed in the same infusion as heparin since a precipitate may form.

7.4.6 Storage and Stability: Mitoxantrone should be stored between 15°C - 25°C (59°F - 77°F).

7.4 **Drug Information on Sorafenib**

7.4.1 Mechanism of Action: Sorafenib is a kinase inhibitor that decreases tumor proliferation *in vitro*. Although in AML conventionally viewed as a FLT3 ITD kinase inhibitor, sorafenib inhibits multiple kinases (c-CRAF, BRAF, mutant BRAF, KIT, FLT-3, RET, RET/PTC, VEGFR-1/2/3, PDGFR- β). Several of these kinases are thought to be involved in tumor cell signaling, angiogenesis, and apoptosis.

7.4.2 Pharmacokinetics: The mean elimination half-life of sorafenib is 25-48 hours. Steady-state plasma concentrations are achieved within 7 days. Following oral administration, sorafenib reaches peak concentrations in approximately 3 hours. With a high fat meal, bioavailability is reduced by 29% compared to that in the fasting state. Sorafenib undergoes oxidative metabolism via hepatic CYP3A4, as well as glucuronidation by UGT1A9. Inducers of CYP3A4 can decrease serum concentration of sorafenib.

7.4.3 Adverse Effects: The most common adverse reactions (> 20%) for sorafenib are diarrhea, fatigue, infection, alopecia, hand-foot skin reaction, rash, weight loss, decreased appetite, nausea, gastrointestinal and abdominal pains, hypertension, and hemorrhage. When used in combination with chemotherapy for treatment of AML, the most common adverse reactions thought to be related to the addition of sorafenib include hyperbilirubinemia/transaminitis, nausea/vomiting, diarrhea, rash, hand-foot syndrome, pancreatitis/colitis, and cardiac/hypertension. Please see Appendix F for management of adverse events specific to sorafenib.

7.4.4 Administration: Subjects will be instructed on the proper administration of sorafenib. Sorafenib tablets should be taken 12 hours apart, at approximately the same time each morning and evening. Sorafenib tablets should be taken without food, at least 1 hour before or at least 2 hours after a meal, and with up to 240 mL (approximately 1 cup or 8 oz.) of water. Consumption of grapefruit and grapefruit juice should be avoided while receiving study drug. If a dose of sorafenib is missed, the next dose should be taken at the regularly scheduled time.

7.4.5 Drug-Drug Interactions: Strong CYP3A4 inducers (such as carbamazepine, dexamethasone, phenobarbital, phenytoin, rifampin, rifabutin, St. John's wort) can decrease systemic exposure to sorafenib, and concomitant use of these medications should be avoided whenever possible. Concomitant use of strong CYP3A4 inhibitors (such as azithromycin, ketoconazole, ritonavir) may be allowed, but patients should be closely monitored for signs/symptoms of toxicity from increased exposure to sorafenib.

Interactions with strong CYP3A4 inhibitors has not been well studied, although ketoconazole administered at 400 mg once daily for 7 days did not alter the mean AUC of a single oral dose of sorafenib 50 mg in healthy volunteers.

7.4.6 Storage and Stability: Sorafenib tablets do not need to be protected from light. They are sufficiently stable with regard to light, oxidation, thermal stress, and hydrolytic degradation. The formulation is presented as an immediate release (IR) dosage form, i.e., the active ingredient is completely dissolved under in vitro test conditions within a short period of time.

7.4.7 Recommended Dose Adjustments for Organ Dysfunction: Mild renal and hepatic dysfunction does not affect the pharmacokinetics of sorafenib, and drug adjustment is not necessary (See Section 6.8.5 for Dose Reduction for Subsequent Cycles.)

8.0 EVALUATION AND END POINT DEFINITIONS

8.1 Treatment Response and Outcome

Treatment response (e.g. morphologic/cytogenetic/molecular complete remission, partial remission) or treatment failure (e.g. resistant disease, aplasia, morphological or molecular/cytogenetic relapse) as well as treatment outcome (e.g. overall survival, relapse-free survival, event-free survival, and remission duration) will be determined by peripheral blood count and bone marrow evaluation and categorized according to criteria recommended by International Working Groups [2, 33]. Patients are routinely assessed for the presence of minimal residual disease (MRD) as detected by multi-parameter flow cytometry and cytogenetic assessment, as per institutional practice.

8.2 Toxicity Criteria

This study will use the CTCAE (NCI Common Terminology Criteria for Adverse Events) Version 5.0 for Toxicity and Adverse Event reporting. A copy of the CTCAE v5.0 can be downloaded from the CTEP home page (<http://ctep.cancer.gov>).

8.3 Definition of Dose-limiting Toxicities (DLTs)

Reported adverse events and potential risks for G-CSF, cladribine, cytarabine, and mitoxantrone, are described in section 7. Dose-limiting toxicities (DLTs) used to guide dose escalation in this trial are defined as follows:

- 8.3.1** Any Grade ≥ 3 non-hematologic toxicity lasting >48 hours that results in >7 day delay of the subsequent treatment cycle, with the exception of febrile neutropenia or infection.
- 8.3.2** Any Grade ≥ 4 non-hematologic toxicity with the exception of febrile neutropenia/infection unless felt to be a direct consequence of treatment-related toxicity (e.g. intestinal infection following mucosal barrier breakdown), and with the exception of constitutional symptoms if no recovery to Grade ≤ 2 within 14 days.
- 8.3.3** Hematologic toxicity with ANC $<500/\mu\text{L}$ or platelet count $<50,000/\mu\text{L}$ for >49 days after initiation of G-CLAM, in conjunction with bone marrow showing no evidence of MRD or persistent AML.

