14.0 STATISTICAL CONSIDERATIONS

14.1 Phase 1

14.1.1 General Considerations: DLTs are defined in Section 8.3. DLTs occurring during Cycle 1 will be used to guide dose escalation. However, before the phase 2 portion is begun, all grade ≥ 3 adverse events of all patients treated in the phase 1 portion will be reviewed to assess for late and cumulative toxicities that were not captured during the phase 1 portion of the trial. The Principal Investigator reserves the right to modify the protocol to reduce the drug doses identified in the phase 1 portion if this assessment suggests a significant risk of late/cumulative toxicities. Patients will be considered evaluable for DLT if they received at least 75% of the assigned doses of each chemotherapeutic during Cycle 1 or if they developed a DLT. If a patient does not develop a DLT but does not receive at least 75% of treatment during Cycle 1, the patient will be considered not evaluable for DLT and will be replaced. Maximum tolerated dose (MTD) is defined as the highest dose studied in which the incidence of DLT is $<33\%$ assuming at least 6 patients have been treated at this dose.

14.1.2 Dose Escalation scheme:

Starting with dose level K=1:

A. Evaluate 6 patients at dose level K

- a. If 0 or 1 have DLT, increase dose to K+1 and go to A
- b. If 2 have DLT, stop dose escalation
- c. If >2 have a DLT, go to dose K-1

The dose level below that which dose escalation was stopped is the potential MTD.

In order to better define safety and initial evidence of anti-leukemia activity while waiting for patients to complete their treatment cycles to assess the MTD, any dose level cohort may be expanded up to 12 patients, provided that

2 or fewer of 6 patients had DLT at that dose level (ie at least 4/6 have had no DLT). the cohort is expanded to 7-11 patients, these patients will not count toward DLT and MTD evaluation. If a cohort is expanded to 12 patients, the following rules will determine further dose escalation:

If 3 or fewer have DLT, increase dose to K+1 (go to A)

If 4 or more have DLT, stop dose escalation

Dose-finding for both mitoxantrone and sorafenib:

Level 1	Mitoxantrone10 mg/m ²	Sorafenib 200 mg BID
Level 2	Mitoxantrone12 mg/m ²	Sorafenib 200 mg BID
Level 3	Mitoxantrone15 mg/m ²	Sorafenib 200 mg BID
Level 4	Mitoxantrone18 mg/m ²	Sorafenib 200 mg BID
Level 5	Mitoxantrone18 mg/m ²	Sorafenib 400mg AM, 200 mg PM
Level 6	Mitoxantrone18 mg/m ²	Sorafenib 400 mg BID

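### Section 8.3.2, read literally, exempts Grade 4 or higher constitutional symptoms that fail to recover and counts those that recover as DLTs; the sentence also allows other readings

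*Combined protocol and SAP*

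**What the plan says.** Section 8.3 of the combined protocol and SAP has three DLT criteria.

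- **8.3.1** covers Grade 3 or higher non-hematologic toxicity lasting more than 48 hours "that results in >7 day delay of the subsequent treatment cycle, with the exception of febrile neutropenia or infection". It has no exception for constitutional symptoms.
- **8.3.2** covers Grade 4 or higher "non-hematologic toxicity with the exception of febrile neutropenia/infection unless felt to be a direct consequence of treatment-related toxicity", and then adds a second carve-out: "with the exception of constitutional symptoms if no recovery to Grade" 2 or lower within 14 days.
- **8.3.3** covers cytopenia persisting beyond 49 days with no leukemia in the marrow.

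Section 14.1.1 refers back to 8.3 for the definition and states that "DLTs occurring during Cycle 1 will be used to guide dose escalation". It says the MTD "is defined as the highest dose studied in which the incidence of DLT is" below 33%, with at least 6 patients treated. Under 14.1.2, for a cohort of 6: "If 0 or 1 have DLT, increase dose to K+1 and go to A"; "If 2 have DLT, stop dose escalation". For a cohort expanded to 12: "If 3 or fewer have DLT, increase dose to K+1"; with 4 or more, escalation stops. No other section restates or corrects the constitutional-symptom clause.

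**The concern.** A recovery condition in a DLT definition normally separates brief events from lasting ones. Here the condition stands directly after the words for constitutional symptoms and inside the exception, so lack of recovery is what earns the exemption. The longer-lasting event is then treated as less dose-limiting than the brief one. The other two criteria in the same section work the opposite way: 8.3.1 counts an event because it lasts and causes delay, and 8.3.3 because it lasts.

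Cycle 1 DLT counts are the formal safety input to escalation. Patients treated at the MTD in phase 1 also count toward the first 19 of phase 2 (14.2), so a miscounted cohort could carry into the efficacy stage.

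**Working it through.** The plan states no figure that depends on this clause, so there is none to reproduce. The check has three parts.

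**1. What each reading of 8.3.2 counts** (Grade 4 or higher; recovery means to Grade 2 or lower within 14 days)

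| Reading | Constitutional, recovers | Constitutional, does not recover | Other, recovers | Other, does not recover |
|---|---|---|---|---|
| A. Literal: the condition limits the exception | DLT | exempt | DLT | DLT |
| B. Lack of recovery brings the symptom back in as a DLT | exempt | DLT | DLT | DLT |
| C. The condition governs the whole criterion | exempt | exempt | not a DLT | DLT |

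Here, other means non-constitutional events outside the febrile neutropenia and infection exception. A and B are opposite for constitutional symptoms. C also changes the treatment of other toxicities.

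**2. What 8.3.1 recovers under reading A**

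An event still above Grade 2 at 14 days is at least Grade 3 and has lasted more than 48 hours. It therefore meets 8.3.1 if, and only if, it delays the next cycle by more than 7 days. It stays uncounted in two situations:

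- It clears without such a delay. Section 6.6 places the marrow at count recovery or Days +28 to +35, whichever is first. For illustration, a symptom starting on Day 5 and lasting 15 days ends on Day 5 + 15 = Day 20, and may delay nothing.
- No further cycle is given, so there is nothing to delay.

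In the other direction, reading A counts recovering constitutional events as DLTs.

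**3. Effect on the escalation decision**

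Thresholds from 14.1.2: 1/6 = 16.7% escalates and 2/6 = 33.3% stops; 3/12 = 25% escalates and 4/12 = 33.3% stops. One patient separates the two decisions in each case.

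The documents give no rate of Grade 4 or higher constitutional symptoms, so the following rates are assumptions. Let b = 20% be the DLT rate from other causes. Let q be the share of patients whose only candidate event is a non-recovering constitutional symptom that 8.3.1 does not catch. Recovering events are set aside. The DLT probability p is b if these events are exempt and b + q if they are counted.

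For 6 patients, P(escalate) = (1 − p)^6 + 6p(1 − p)^5:

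- p = 0.20: 0.262 + 0.393 = 0.655
- p = 0.22: 0.225 + 0.381 = 0.606
- p = 0.25: 0.178 + 0.356 = 0.534
- p = 0.30: 0.118 + 0.303 = 0.420 (from unrounded terms)

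For 12 patients, P(escalate) = P(X ≤ 3), with X binomial(12, p).

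| q | 6 patients, exempt | 6 patients, counted | 12 patients, exempt | 12 patients, counted |
|---|---|---|---|---|
| 2% | 0.655 | 0.606 | 0.795 | 0.739 |
| 5% | 0.655 | 0.534 | 0.795 | 0.649 |
| 10% | 0.655 | 0.420 | 0.795 | 0.493 |

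Now let r be the share of patients whose only candidate event is a recovering constitutional symptom. Reading A gives p = b + r and reading B gives p = b + q. Reading A makes escalation more likely than B if q exceeds r, and less likely if r exceeds q. Nothing in the documents fixes either share.

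**The case against.** The strongest reply is that the sentence is clumsy and any investigator would see the intent. The first carve-out in 8.3.2 exempts a category unless a condition brings it back, and the second can be read in parallel (reading B). That reading is plausible, but the text does not select it. A definition used to adjudicate DLTs should not depend on readers setting its words aside.

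A second reply is that other provisions limit the damage, and this stands in part. A reader might infer that the clause lets the worst events escape altogether. It does not, because 8.3.1 has no constitutional exemption, and the recovery conditions before further courses (6.0 Study Overview, 6.8.2) mean that some persistent events will cause the delay that 8.3.1 requires. Nor are DLT counts the only thing bearing on the dose taken forward. Section 14.1.1 calls for review of all Grade 3 or higher adverse events before phase 2 and lets the Principal Investigator reduce doses, and 14.1.2 adds an efficacy rule. The review is a discretionary backstop, however, and leaves cohort DLT counts as they were.

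Third, 14.1.2 allows a cohort with 2 DLTs in 6 to be expanded to 12, so a stop at 2/6 need not be final. The 12-patient rule has its own one-patient boundary.

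Fourth, the toxicities that Section 1.0 reports as common with these drugs do not single out constitutional symptoms, so such events may be rare. That limits the likely size and does not repair the wording.

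**Conclusion.** The clause is wrong as written. Its literal reading is inverted and conflicts with 8.3.1 and 8.3.3, and the alternative readings give different DLT definitions. The gap consists of events unresolved at 14 days that clear without a delay of more than 7 days, or after which no further cycle is given, together with recovering events counted as DLTs.

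A reader might go further and infer that escalation is biased upward, or that the MTD was misjudged. The documents support neither. They report no such event and no rate, and the two kinds of misclassification pull in opposite directions. The illustrated drop of 0.049 to 0.235 in the chance of escalating with 6 patients (0.655 − 0.606 and 0.655 − 0.420) rests on the assumed 20% base rate and on 2% to 10% of patients having an uncaptured event. At the low end the effect is small. What is firm is that one patient can decide a cohort and that this definition does not classify that patient unambiguously.

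**What to change.** The sponsor should confirm which rule was intended and reword 8.3.2 so that it has one reading, states plainly which events the 14-day recovery condition applies to, and is reconciled with 8.3.1. The choice of rule is the sponsor's. The study file should record which reading was used for phase 1 DLT calls, and any adjudication that depended on the clause should be re-checked against the confirmed rule. If reading C was applied, the re-check must extend to non-constitutional Grade 4 or higher events.

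The cost is one clause in an amendment and a file review, with no added patients or procedures. If no event depended on the clause, the re-check closes at once.
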